8. Presence of ferromagnetic objects in the body that are contraindicated for MRI of the head, fear of enclosed spaces, or other standard contraindication to MRI (self-report checklist).
9. Cannot lie comfortably flat on his/her back for up to 2 hours in the MRI scanner (self-report).
10. Body weight > 550 lbs. The MR scanner bed is tested to a weight limit of 550 lbs.
11. Milk or soy allergy (self-report).

Note that subjects will not be excluded on initial screening from enrollment onto this study if their breath alcohol test is positive; or if their urine test is positive for drugs. The following guideline will be followed for positive alcohol/drug screens on study procedure days:

- If an AUD subject's breath alcohol and/or urine drug screen test is/are positive on study days (i.e., within 24 hours before study procedures except for benzodiazepines during detox, including oxazepam [™Serax]), the procedures will be postponed and rescheduled to another day. If the urine drug screen is positive for THC-COOH, a saliva drug screen will be performed and subject may proceed with MRI/NPT procedures if saliva results for THC are negative. We will not place a limit on rescheduling study days.

4. Study Design and Methods

a. Study overview

This study includes an inpatient component and outpatient follow-up.

Patients are admitted to the Clinical Center (CC) for detoxification and treatment as usual (TAU) under protocol 14-AA-0181. Under the current protocol, patients will be randomized into a meal and shake plan consisting of either a standard American (SA) versus a ketogenic diet (KD). Patients will be given benzodiazepines only if withdrawal symptoms emerge while receiving either the KD or the SA diet. Subjects may be administered benzodiazepines only if withdrawal symptoms emerge. On day 2-6 after admission, all patients will undergo an MRI (brain structure, functional reactivity, functional connectivity and MRS) and will have a battery of neuropsychological tests (NP). Personality tests will be obtained during week 1 at the time of NP testing. The MRI scans will be repeated at 1 week intervals (Week 2 and 3). The Sleep Profiler device will be obtained 2X p/week in weeks 1-3. The ™GENEActiv (actigraphy) will be done for an entire week in weeks 1 and 3. The NP studies will be repeated coincident with the last MRI session. We will complete studies on at least 25 alcoholics with the ketogenic diet and 25 with the regular diet.

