The first step for our screening is to obtain informed consent for 14-AA-0181 prior to any procedures being implemented. Subjects will undergo a comprehensive medical history and physical examination by a clinically credentialed licensed independent practitioner. The purpose of the medical history and examination is to rule out serious medical conditions that may be contraindications to protocol participation. A copy of the medical evaluation will be placed in the subjects NIH chart. Screening procedures will include: Demographics; vital signs including height, weight and temperature; standard laboratory tests (Chem Screen, CBC, and Urinalysis); STAT urine tests to identify drug abuse and NP testing; a urine pregnancy test for females who are able to become pregnant; and an EKG. We will also interview the subject to obtain a lifetime drug history (including but not limited to everything from caffeine, tobacco, alcohol, and common illicit drugs) and we will administer self-report questionnaires, which provide descriptive data necessary to our brain imaging program. Some of the self-report assessments will be administered to evaluate the inclusion of participants as well as to provide descriptive data in all of our subjects. It is possible that subjects could be excluded from the ketogenic diet study based on the information they provide to us. If on the 14-AA-0181 admission and screening day the subject agrees to participate, they are given the informed consent for the ketogenic diet study.

e. Study procedures

Study Timeline: After admission and initial 14-AA-0181 screening, AUD patients who agree to participate will first sign the consent for this study and then begin to undergo detoxification in the 1SE unit under 14-AA-0181. The current protocol will involve being randomized into one of two diets. One diet consists of a ketogenic diet (KD) snacks and shakes 3x p/day (high in fat). The other liquid diet consists of a standard American (SA) diet shakes 3x p/day in the proportions of carbohydrates, protein and fat of traditional western diet. SA will receive the same KD solid snacks, in order to keep the diets blind to participants. Both diets will be eucaloric such that a standard equation based on weight, height, sex and

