age will be used to determine how many calories are provided to each participant. While on the KD/SA diet, patients are limited to drink non-caloric drinks (water, diet soda, coffee and tea without milk or sugar). In addition to the diets, MRI/fMRI/MRS scans, genetic tests, self-report ratings, motor activity, sleeping behavior, NP testing and personality measures will be obtained in all participants. The first MRI session and the first NP testing will be performed within the first 2-6 days of admission. The MRI sessions will be repeated on a weekly basis (second and third week of hospitalization; the later corresponding to the last week of their inpatient stay) and the NP testing will be repeated during the third week of hospitalization. MRI scanning session and NP tests are described below and are for research purpose only.

During the inpatient period, participants will be periodically monitored for signs of withdrawal and evaluated for mood, sleep and alcohol cravings. Compliance with diet adherence (KD or SA) will be closely monitored during the hospital stay using daily urine tests.

After the final MRI sessions, the study diets are discontinued and the individual blind will be broken on a per subject basis. If KD is discontinued this will be done by slowly increasing the levels of carbohydrates to the diets of the SA group [68]. The levels of carbohydrates in the control group remains constant throughout the study, but patients are still blind to treatment group.

Participants will then be released at about 3-4 weeks from the Clinical Center and will have a 3 month follow up period under this protocol which is discussed below in section 4.d.12 *Follow-Up*.

1. Ketogenic Diet (KD) / Standard American (SA) Snacks and Shakes: Participants will be randomized to a meal plan of either a ketogenic diet (KD) or standard American (SA) diet at the time they sign the consent (day 1 or 2 of admission). For each meal at breakfast, lunch and dinner, the diets will consist of SA meal (carbohydrate rich) or KD meal depending on treatment randomization. Compliance tests are done daily with urine tests measuring ketone levels by an independent person (BSN RN) [69], results of which are retained. To ensure that the diet is double blind in both the outpatient and inpatient phases, solid snacks are always ketogenic and shakes are either KD or SA.

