We will collect DNA so that in the future when new findings emerge with respect to genes implicated in brain diseases so we can assess across integrated data from various brain imaging studies if they are associated with changes in brain connectivity. However, DNA collection will be optional and will not exclude subjects from participating in this study if they do not want to give blood for genotyping.

b. Data including genomic data and sample sharing plan

Samples and data, including genomic data may be shared with collaborators.

The following questionnaires/assessments/interviews collected under the 14-AA-0181 will be shared with this protocol: Smoking History Questionnaire [98]; Fagerström Test for Nicotine Dependence (FTND) [99]; The Timeline Follow-Back (TLFB) [100]; Alcohol Use Disorders Identification Test (AUDIT) [101]; Barratt's Impulsivity Scale (BIS-11) [102]; Structured Clinical Interview (SCID) for DSM-IV or DSM 5 [103]; Alcohol Dependence Scale (ADS) [104]; and Clinical Institute Withdrawal Assessment – Alcohol revised (CIWA-Ar) [105].

Data and samples may also be shared with collaborating laboratories at NIH or outside of NIH and/or submitted to NIH-designated repositories and databases if consent for sharing was obtained. Repositories receiving data and/or samples from this protocol may be open-access or restricted access.

Samples and data will be stripped of identifiers and may be coded (“de-identified”) or unlinked from an identifying code (“anonymized”). When coded data is shared, the key to the code will not be provided to collaborators, but will remain at NIH. Data and samples may be shared with investigators and institutions with an FWA or operating under the Declaration of Helsinki (DoH) and reported at the time of continuing review. Sharing with investigators without an FWA or not operating under the DoH will be submitted for prospective IRB approval. Submissions to NIH-sponsored or supported databases and repositories will be reported at the time of Continuing Review. Submission to non-NIH sponsored or supported databases and repositories will be submitted for prospective IRB approval.

Required approvals from the collaborating institution will be obtained and materials will be shipped in accordance with NIH and federal regulations.

6. Additional Considerations

a. Research with investigational drugs or devices

N/A

7. Risks and Discomforts

Potential risks from this study include the following:

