- At the discretion of the Principal Investigator (PI) and Medical Investigator, based on adverse event (AE) severity
- Non-compliance with protocol procedures or investigator request(s)
- Patient request

9. Outcome Measures

a. Primary outcome measures:

To assess ketogenic diet on:

1. Withdrawal ratings (CIWA) and Benzodiazepine use during withdrawal in the first week of detoxification.
2. Brain function (during rest and activation assessed with fMRI), neurochemistry (assessed with MRS) and structure (assessed with MRI).
3. NP performance.

b. Secondary outcome measures

To determine if ketogenic diet improves:

1. sleep.
2. mood.
3. alcohol craving.

10. Statistical Analysis

a. Analysis of data/ study outcomes

Withdrawal symptoms: We will use the CIWA-Ar to measure alcohol withdrawal, which will be measured daily [106, 107]. Because there are no studies on the KD on withdrawal symptoms we cannot predict the effect size to be expected. We will compare the scores on the CIWA-Ar between participants on the KD and participants on the control diet. Based on effects of medications used for treatment of withdrawal symptoms we expect a 30 % reduction in CIWA-Ar scores with KD [108].

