Empirical knowledge regarding the necessary sample size for significant effects of a ketogenic diet on withdrawal, NP or brain functioning in AUD during withdrawal does not exist. Previous behavioral and pharmacological treatment studies in AUD with behavioral, fMRI and MRS as outcome measures have studied on average 20-25 patients per group [treatment versus control: reviewed in 109]. Clinical efficacy of a ketogenic diet in epilepsy was established in randomized-controlled trials in 20 [55] or 94 epilepsy patients [56]. In 20 elderly participants, an acute dose of ketogenic meal improved executive functioning 1.5-3 hours after, as compared to a control meal on a different day [58]. Further, beneficial effects of KD on sleep was established in a study in 18 children with epilepsy [57]. Thus, for within-subject fMRI studies in individuals with AUD sample sizes of 25 patients per group have been effective for obtaining interpretable data regarding behavioral and neurocognitive effects of treatment, suggesting that the sample size of the current protocol is adequate for the identification of effects of ketogenic diet in AUD.

Independent sample t-test will be used to test **Hypothesis 1**, “withdrawal symptom severity within the first week of detoxification will be lower for patients with KD compared to control diet”.

Paired t-test on BOLD signals will be used to test **Hypothesis 2**, “limbic activation to alcohol cues would be reduced after 3 weeks of treatment”; **Hypothesis 3**, “the functional connectivity of the saliency network will be stronger after 3 weeks of treatment”; **Hypothesis 4**, ‘prefrontal cortex atrophy and ventricular enlargement will stronger decrease after 3 weeks of KD treatment compared to control diet’. Assuming a threshold probability for rejecting the null hypothesis (Type I error rate), $\alpha = 0.05$, and a probability of failing to reject the null hypothesis under the alternative hypothesis (Type II error rate), $\beta = 0.2$, the

proposed sample sizes (25 KD versus 25 ND) will allow us to detect an effect size of 0.66.

To test KD treatment effects, mixed ANOVAs will be used to assess whether KD group shows reduced brain activation (Hypothesis 2), higher functional connectivity (Hypothesis 3), and prefrontal cortex atrophy and ventricular enlargement (Hypothesis 4) compared to the control diet group. Assuming $\alpha = 0.05$ and $\beta = 0.2$, the proposed sample sizes will allow us to detect an effect size of 0.9.

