consent process in accordance with NIH policy. Only subjects that can give informed consent will be included in this study. The PI and/or AI's will determine that the subjects are able to give informed consent based on their clinical assessment of the subject's ability to understand the nature of the study and the risks. If patient's BAL is more than 0 and/or if their CIWA is more than 8 at the time of consent, or if the subject's capacity to consent remains otherwise questionable, the Ability to Consent Assessment team (ACAT) will be consulted. HSPU advocates will monitor the informed consent discussion conducted between investigator and subject assessing subject capacity to enroll in the study and providing ongoing monitoring over the course of research participation. Co-workers will not consent each other if possible, but if a coworker does consent another, HSPU will monitor the consent process.

c. Consent documents

The consent form contains all required elements. The original consent is filed with their NIH medical record and a digital copy is uploaded into the CRIS system. A copy of the signed consent is also made for the subject's research binder for regulatory purposes.

14. Data and Safety Monitoring

a. Data and safety monitor

Data and safety monitoring will be monitored by the PI, who will review all safety data for each participant. The PI will consult with the Medically Accountable Investigator (MAI) should any concerns about safety arise.

b. Data and safety monitoring plan

This study will be monitored on a yearly basis at the time of continuing review. We will look at possible trends in AE's and UP's to determine if a change to the protocol/consent/study procedures becomes necessary via study amendment. In addition, individual subject case report forms will be monitored on an ongoing basis upon completion of study visits. Frequency of monitoring may increase if the PI determines it is necessary.

c. Criteria for stopping the study or suspending enrollment or procedures

This study will be stopped and enrollment suspended if any serious adverse events occur that is determined to potentially be related to one of the study procedures.

15. Quality Assurance (QA)

a. Quality assurance monitoring

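### Hypothesis 1 (first-week CIWA-Ar) is tested without baseline adjustment, although a pre-diet CIWA score appears to exist and could be the one prespecified covariate

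*Combined protocol and SAP*

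**What the plan says.** Section 9.a makes first-week CIWA ratings a primary outcome. Section 10.b gives the test: "Independent sample t-test will be used to test" Hypothesis 1, that withdrawal severity in the first week is lower on the ketogenic diet. Section 10.a plans a comparison of CIWA-Ar scores between diets and describes the "CIWA-Ar to measure alcohol withdrawal, which will be measured daily". It does not say which summary of the daily scores is analysed. On the effect, it states that "we cannot predict the effect size to be expected".

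A pre-diet score can be inferred from four places:

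- Section 13.b sends a patient for a capacity assessment if the patient's "BAL is more than 0 and/or if their CIWA is more than 8 at the time of consent", so a CIWA value must be known at consent.
- Section 4.e says that patients "will first sign the consent for this study and then begin to undergo detoxification".
- Section 4.e.1 places randomisation "at the time they sign the consent (day 1 or 2 of admission").
- Section 5.b lists the measures shared from the screening protocol 14-AA-0181, including "Alcohol Dependence Scale (ADS) [104]; and Clinical Institute Withdrawal Assessment".

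None of these defines a baseline CIWA for analysis, and the procedures table in section 4.a has no CIWA row. Section 10.a has one covariate rule: age and severity of addiction are added if randomisation leaves the groups different on them. The rule comes directly after the imaging and spectroscopy text, and it is unclear whether it reaches Hypothesis 1. It does not mention CIWA.

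**The concern.** When an outcome is also measured before treatment, adjusting for that value removes the part of the outcome variance it predicts. A two-sample t-test leaves that variance in the error term. In a trial planned for 25 completers per arm, with about half of those recruited not expected to complete, this precision may be available at no cost in patients.

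The conditional rule in section 10.a does not fill the gap. It names other variables, gives no criterion for a difference, and leaves the model to be settled after the arms have been compared. Bias is not at stake: the t-test is valid under randomisation. What is at stake is power, and discretion over the model for a primary outcome.

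**Working it through.** **The plan's own figure.** Section 10.b attaches no detectable effect to Hypothesis 1. The nearest is 0.66, given with the paired tests at alpha 0.05 and beta 0.2. At 25 per arm a two-sided two-sample t-test detects 0.81 with 80% power, and a paired test with n = 25 detects 0.58. The figure of 0.66 is matched by a paired test with n = 20 (0.660). It is used below only as an illustrative effect size.

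**Inputs.** From the documents: alpha 0.05; power 80%; 25 per arm (section 10.b); an initial 3:2 allocation (section 4.e.2); more than 25 per group expected for Hypothesis 1 (section 10.b). Assumed: a two-sided test, and r of 0, 0.2, 0.3, 0.5 or 0.7.

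**Formulas** (noncentral t, effect d in SD units, N = n1 + n2):

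- t-test: df = N − 2; noncentrality = d / √(1/n1 + 1/n2).
- ANCOVA, one covariate: df = N − 3; noncentrality = d / √[(1/n1 + 1/n2)(1 − r²)(1 + 1/(N − 4))]. The last factor charges for chance imbalance in the covariate.

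**Worked case: 25 per arm, d = 0.66, r = 0.5.**

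- t-test: 0.66/√0.08 = 2.33 on 48 df; power 62.8%.
- ANCOVA: 0.66/√(0.08 × 0.75 × 47/46) = 2.67 on 47 df; power 74.2%.

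**Power at d = 0.66:**

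| Arms | t-test | r=0 | r=0.2 | r=0.3 | r=0.5 | r=0.7 |
|---|---|---|---|---|---|---|
| 25+25 | 63% | 62% | 64% | 66% | 74% | 89% |
| 30+20 | 61% | 60% | 62% | 64% | 73% | 87% |
| 30+30 | 71% | 70% | 72% | 74% | 82% | 94% |

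**Detectable d at 80% power, 25 per arm:** 0.81 for the t-test; 0.82, 0.80, 0.78, 0.71 and 0.58 for ANCOVA at r = 0, 0.2, 0.3, 0.5 and 0.7.

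**Equivalent size.** To match ANCOVA with 25 per arm at d = 0.66, the t-test needs 26, 27, 33 or 47 per arm at r = 0.2, 0.3, 0.5 or 0.7.

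**Break-even.** ANCOVA has more power than the t-test above r of about 0.15 with 50 patients, or 0.13 with 60.

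**Simulation check (20,000 runs, 25 per arm).** At d = 0.66, t-test and ANCOVA power are 62.6% and 61.5% at r = 0, 62.8% and 65.9% at r = 0.3, and 62.5% and 74.1% at r = 0.5. Under the null at r = 0.5, type I error is 4.9% and 5.1%.

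**Adjusting only on imbalance.** Suppose the section 10.a rule were extended to baseline CIWA with an assumed trigger of p < 0.05, since the plan gives none. In 40,000 simulated trials (25 per arm, r = 0.5, d = 0.66), power is 62.9% for the t-test, 74.5% for always adjusting and 63.5% for adjusting on imbalance. The conditional rule recovers almost none of the gain.

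**Why one covariate.** With three covariates and 25 per arm, power is 59.9% at a multiple correlation of 0 and 61.6% at 0.2. It passes the t-test only above about 0.26.

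**The case against.** The strongest reply is that nothing is wrong: the t-test is valid, and the proposed covariate is inferred, not documented. Section 13.b mentions CIWA only as a trigger for a capacity review. Detoxification itself runs under 14-AA-0181, so the CIWA-Ar data shared in section 5.b could be the daily outcome scores. This stands, and is why the recommendation depends on confirming the score.

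The second reply is that r is unknown and probably low. Consent can take place with alcohol still in the blood, before withdrawal has developed. Consent on day 1 or 2 means the score is taken at different stages of withdrawal. Section 4.a says "Patients will be given benzodiazepines only if withdrawal symptoms emerge while receiving either the KD or the SA diet", so later scores may be altered by medication. This also stands. At r of 0.2 to 0.3 the gain is only 1 to 3 points, and the larger gains need correlations that nothing in the documents supports.

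Third, the setting is illustrative. The 0.66 belongs to other tests, and more week-1 completers would shrink the gain. At an assumed 40 per arm the t-test has 83% power, against 84%, 86% and 92% for ANCOVA at r = 0.2, 0.3 and 0.5. With d = 0.3 and 25 per arm, power is 18.0% for the t-test and 18.3% or 19.0% for ANCOVA at r = 0.2 or 0.3, which is immaterial.

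Fourth, this is a late amendment, and individual blinds are broken as patients finish. The documents do not give accrual or unblinding status, so whether a change now would still count as prespecified cannot be judged from them.

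What remains is the asymmetry: about one point of power lost if r is 0, and about 11 points gained if r is 0.5.

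**Conclusion.** The point holds as an efficiency and prespecification matter, at the level of something to consider. The plan names only a t-test for Hypothesis 1. The one covariate rule that might reach it is conditional, undefined and does not mention CIWA. A pre-diet CIWA probably exists but is not guaranteed.

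At 25 per arm and d = 0.66, one always-included covariate changes power by about −1, +1, +3, +11 or +26 points at r of 0, 0.2, 0.3, 0.5 or 0.7. These figures rest on an assumed r, an illustrative effect size and a two-sided test. Given the reasons to expect a low r, the lower part of that range deserves the most weight. Confidence is medium. Baseline adjustment does not remove any effect of symptom-triggered benzodiazepines on the scores.

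**What to change.** - Replace the t-test for Hypothesis 1 with a prespecified ANCOVA of first-week CIWA-Ar on diet arm, with the last CIWA-Ar before diet start as the single, always-included covariate.
- Name the one first-week summary to be analysed, for example the mean of the daily scores. The plan does not name one, and r depends on it.
- Confirm that the pre-diet score is recorded for every randomised participant, and fill any missing value with the pooled mean so that nobody is dropped.
- State that the group-difference rule in section 10.a does not govern this analysis. Age and a severity score need not be mandatory covariates.
- Record when the change was made relative to any unblinded look at CIWA data.

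The cost is SAP wording, the confirmation above and one degree of freedom. If r is 0, power at d = 0.66 with 25 per arm falls from 63% to 62%. No extra patients or visits are needed if the score is already recorded.

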More recently studies using resting functional connectivity (RFC), showed disrupted connectivity in the default mode network (DMN) [47], and in the saliency network in alcoholics [48]. Magnetic Resonance Spectroscopy (MRS) can quantify a variety of neurochemicals, including various neurotransmitters and their byproducts (glutamate, glutamine and GABA) constituents of metabolic pathways (choline and creatine) as well as the glial marker myo-inositol (mI) [49]. In recently detoxified alcoholics, higher concentrations of mI in thalamus, anterior cingulum and prefrontal white matter [50] have been reported when compared to controls. However, to our knowledge there are no studies that have assessed if these changes recover with detoxification.

These studies provide evidence that chronic alcohol impairs brain structure and function and cognitive performance but they also indicate that some of these changes recover with detoxification. We hypothesize that some of the cognitive structural and functional changes reported in alcoholics reflect the effects of energy substrate deprivation that follows withdrawal from alcohol. Here we will test if a ketogenic diet can protect the brain from the negative effects of energy deprivation that we hypothesize occurs during alcohol detoxification. We hypothesize that this will result in a faster recovery of brain function.

Ketogenic Diet

Ketogenic diets are based on foods high in fat but very low in carbohydrates. Ketogenic diets are approved non-pharmacological interventions for the treatment of child epilepsy [51, 52], [Metanalyses:53, 54]. In addition to the clinical efficacy of a ketogenic diet in epilepsy in decreasing seizures [55, 56], the diet has also been shown to improve sleep in children with epilepsy [57], and improved executive functioning in elderly healthy volunteers [58]. There is also increased interest on the value of ketogenic diets for other conditions, including diseases of substrate insufficiency or of insulin resistance, diseases of free radical damage and disorders of hypoxia [59], and preliminary evidence suggests a potential therapeutic role of ketogenic diets in brain and other cancers, hypoxia or ischemic encephalopathy, stroke, heart failure,

Alzheimer's, Parkinsonism, amyotrophic lateral sclerosis, diabetes, autism, inflammatory disorders, migraine, severe hyperactivity [60, 61, 62].

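### Section 10.b gives Hypotheses 2–4 both a paired t-test and a mixed ANOVA without saying which decides, and the paired test cannot test Hypothesis 4

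*Combined protocol and SAP*

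**What the plan says.** Section 10.b (Power analysis) deals with Hypotheses 2–4 twice.

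The first paragraph states "Paired t-test on BOLD signals will be used to test" all three of them. Hypothesis 2 expects a smaller limbic response to alcohol cues at three weeks, and Hypothesis 3 expects stronger saliency-network connectivity by then. Neither names a comparison diet. The fourth does, and concerns brain structure: "prefrontal cortex atrophy and ventricular enlargement will stronger decrease after 3 weeks of KD treatment compared to control diet".

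For this paragraph the plan quotes a detectable effect of 0.66 at alpha 0.05 and 80% power, printed next to the two arm sizes of 25.

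The second paragraph begins "To test KD treatment effects, mixed ANOVAs will be used to assess whether KD group shows reduced brain activation". It goes on to list Hypotheses 3 and 4 as well, all against the control diet, with a detectable effect of 0.9 at the same alpha and power.

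Section 9 makes fMRI and structural MRI primary outcomes. The Introduction reviews imaging and cognitive changes in alcoholics and says of the studies reviewed that "they also indicate that some of these changes recover with detoxification".

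**The concern.** Three things in these two paragraphs do not fit together.

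1. **Hypothesis 4 has a test that cannot answer it.** It claims a larger change on KD than on the control diet. A paired test compares a patient with himself or herself and contains no diet contrast. Atrophy and ventricular size are also structural measures, so a test on BOLD signals does not bear on them.
2. **Hypotheses 2 and 3 have no comparator.** They assert a change after three weeks of treatment. Every patient is detoxified and receives usual treatment during those weeks, and the background expects some recovery with abstinence. A paired test can therefore support either hypothesis when the diet does nothing.
3. **Nothing says which test decides.** Each hypothesis carries two tests with two detectable effects. A mixed ANOVA itself yields group, time and group-by-time terms, and none is named. The time term has the same weakness as the paired test. Section 10.a does not settle this: for fMRI it allows within-subject t-statistics and never names KD versus SA as the contrast.

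At stake is whether a primary imaging hypothesis is reported as supported because of the diet or because of a time trend common to both arms.

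**Working it through.** **Inputs from Section 10.b:** alpha 0.05, power 80%, 25 completers per arm, detectable effects 0.66 (paired) and 0.9 (mixed ANOVA).

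**Assumptions:** two-sided tests (sidedness is not stated). Effect sizes are in SDs of the change score. The mixed ANOVA is taken on two scans, so that its group-by-time term equals a two-sample t-test on change.

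**Step 1: the plan's own figures.**
- Paired test: noncentral t, n − 1 df, noncentrality d√n. The normal approximation for the detectable d is (1.960 + 0.842)/√n. At n = 25 this is 2.802/5 = 0.560; the exact value is 0.584.
- Between-diet test of change: noncentral t, 2n − 2 df, noncentrality d√(n/2). The approximation is 2.802 × √(2/25) = 0.792; the exact value is 0.809.

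| Per arm | Paired, detectable d | Between-diet, detectable d |
|---|---|---|
| Printed, for 25 | 0.66 | 0.9 |
| 25 (exact) | 0.584 | 0.809 |
| 20 (exact) | 0.660 | 0.909 |

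Neither printed figure is reproduced at 25. Solving back gives n = 20.0 for 0.66 and 20.4 per arm for 0.9. One-sided testing does not explain the gap (0.512 and 0.713 at 25). The discrepancy is conservative: at 25 per arm, power is 88.6% for a paired effect of 0.66 and 87.7% for a between-diet effect of 0.9.

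**Step 2: what 0.66 means for the diet comparison.** Read as a between-diet effect at 25 per arm, 0.66 has noncentrality 0.66 × √12.5 = 2.33 and power 62.8%. About 37 per arm would be needed for 80%.

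**Step 3: no diet effect, same recovery in both arms.** The documents give no recovery size, so a range is assumed. The KD-arm paired test has 24 df and noncentrality 5 × recovery.

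| Assumed standardized recovery | Noncentrality | KD-arm paired test rejects (n = 25) | Between-diet test rejects |
|---|---|---|---|
| 0.3 | 1.5 | 30.2% | 5.1% |
| 0.5 | 2.5 | 67.0% | 5.0% |
| 0.66 | 3.3 | 88.6% | 5.0% |

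The last column is from simulation (20,000 runs). In the same runs the paired test rejected 29.7%, 67.1% and 88.7% of the time, in line with the formula. The plan does not say whether the paired test uses the KD arm or both arms pooled. Pooled (n = 50), it rejects 54.8%, 93.4% and 99.6% of the time.

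**The case against.** The strongest reply is that the diet effect already has its own test. The second paragraph of Section 10.b assigns it to mixed ANOVAs against the control diet, for all three hypotheses, with a separate detectable effect. On that reading the paired tests describe change over time, the ANOVAs address the diet, and Hypotheses 2 and 3 as literally worded assert no diet difference. The rejection rates in Step 3 are then simply the power to detect a real within-person change. Section 10.a also provides for structural image processing, so Hypothesis 4 would not in practice be analysed on BOLD.

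Much of this stands. A reader might infer that the plan credits ordinary recovery to the diet, or that it lacks a between-diet test. The documents support neither: nothing says a paired result will be read as a diet effect, and no rule compares a significant KD arm with a non-significant SA arm. It would also overstate the background to say that all these measures recover. It says some do, and for saliency-network connectivity (Hypothesis 3) it reports disruption but no recovery.

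Three points survive. The paired test is stated to test the hypotheses, not to describe change. Hypothesis 4 is on that list although a paired test cannot address it. And no sentence ranks the two tests or names the deciding ANOVA term.

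**Conclusion.** The point holds as a correction to a stated analysis of primary imaging outcomes. For Hypothesis 4 the paired BOLD assignment is wrong as written. For Hypotheses 2 and 3 the missing comparator and the unranked pair of tests leave open that a time effect shared by both arms decides them.

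The size is conditional. If the KD-arm paired result were taken as the diet test, with no diet effect and recovery of 0.3 to 0.66 SD, it would reject in 30% to 89% of trials, against 5% for the between-diet test. These rates rest on assumed recovery sizes, two-sided testing and 25 completers in the arm. They do not describe an error rate of the planned mixed ANOVA.

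The printed 0.66 should not be read as the trial's sensitivity to a diet effect. At 25 per arm the between-diet test of change detects about 0.81. Both printed figures match about 20 per arm.

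**What to change.** Change the wording of Section 10.b only:

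- Remove Hypothesis 4 from the paired BOLD list and test it on structural volumes.
- Word Hypotheses 2 and 3 as KD versus SA.
- State that Hypotheses 2–4 are each decided by the group-by-time term of the mixed ANOVA, and name the scans that enter it. The first scan (days 2–6) may fall after the diet has started (randomization on day 1 or 2), so the text should say that the term measures change from that scan.
- Label paired within-person changes as descriptive.
- Quote a detectable effect only for the between-diet test, recomputed at 25 per arm: about 0.81, two-sided, for a two-scan comparison. State the sidedness.

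No patients, scans or procedures are added. The cost is that the more favourable-looking 0.66 is no longer quoted. The between-diet figure itself improves from 0.9 to about 0.81 once computed at the stated sample size.
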